**Evaluation of Wear Experience with Daily Disposable Water Surface Contact
lenses in habitual Comfilcon A contact lens wearers**

NCT 05096156

Evaluation of Wear Experience with Daily Disposable Water Surface Contact lenses in habitual Comfilcon A contact lens wearers

[name], OD MS

The Ohio State University College of Optometry
Innovation in Vision and Eye care Research Group - iVERG

Purpose

The purpose of this study is to explore the wear experience of current Comfilcon A (Biofinity®) contact lens wearers after they have been fit into Verofilcon A (PRECISION1®) Contact Lenses.

Study Overview

This open-label study is of current Biofinity® (Cooper Vision, San Ramon, CA, USA) contact lens wearers who are satisfied with their lenses. Subjects will be refit into PRECISION1® contact lenses and will wear lenses for approximately 2 weeks. Subjects will return for vision and lens fit assessments and will complete surveys about their wear experience.

Background

Soft daily wear contact lenses are used by an estimated 40.9 million adults in the United States.¹ Contact lenses which are worn for daily wear are considered minimal risk by the FDA, and risks to wearers are minimized by proper lens care and hygiene. Daily disposable contact lenses do not require daily cleaning and overnight storage, which improves the required amount of time to care for contact lenses. In addition, daily disposable contact lenses are associated with less lens deposits, which decreases associated comfort issues in lens wearers, including decreasing the risk of triggering Giant papillary conjunctivitis (GPC) and/or ocular allergic responses in patients.² Additionally, daily disposable contact lens wearers are not likely to expose their lenses to water and tend to have better lens hygiene since these lenses do not require daily cleaning. This is reflected in a study which found less superficial punctate staining and symptoms of dryness when comparing daily disposable contact lens wear with planned replacement lenses.³ The subjects in this study are current satisfied wearers of 1 month planned replacement lenses (Biofinity®) and will be fit into PRECISION1 daily disposable contact lenses, which are less likely to be associated with the already minimal risks of daily contact lens wear.

Key Endpoints:

- Subjective assessment of P1 with CLDEQ-8

- Visual Analog Scale survey of lens wear symptoms (comfort, dryness, vision)
- Assessment via questionnaire about quality of life, preference, and lens modality experience

Study Time Points:

Visit 1 will be conducted to consent the subject and determine eligibility. Consenting will be conducted via phone call and REDCap and will occur before the subject arrives on site if possible. The participant will verify their current prescription with Biofinity lenses and answer questions about ocular health to further determine eligibility. Participants will also verify that they are happy with their current lenses. Upon reporting to the in-person portion of the visit, visual acuity and an evaluation of the subject's ocular health will occur. Biofinity® lenses will be evaluated and optimized before dispensing a new pair of lenses for approximately 1 week of wear.

Visit 2: Biofinity® contact lens follow up and Precision 1 fitting visit. Patients will verify that they are still satisfied with their current Biofinity® contact lenses in order to proceed and vision, lens fit and ocular health will be assessed. Subjects will then be fit with PRECISION1® Contact Lenses and will complete assessments of initial satisfaction, initial comfort, and initial vision using REDCap. Lenses will be dispensed and a contact lens follow-up visit will be scheduled.

Visit 3: The contact lens follow up visit will occur approximately 2 weeks (± 3 days) following the PRECISION1 lens fitting. Subjects will have visual acuity, an assessment of ocular health, and lens fit completed. Subjects will then complete surveys about their lens wear experience.

Surveys will be completed using REDCap and include:

- CLDEQ-8
- VAS survey of comfort/dryness/vision on a 0 to-100 scale:
 - Overall Quality of vision
 - End of Day Quality of vision
 - Overall comfort
 - End of Day comfort
 - Overall dryness
 - End of Day dryness
- Quality of life/preference, lens modality experience
- Convenience of daily disposable, preference for daily disposable, ease of use
- Satisfaction with P1

Recruitment

Potential subjects may see posters placed on bulletin boards at The Ohio State University or local eye care offices, emails to students, faculty and staff at OSU, online or paper ads, or signs on the OSU buses. A

search of the electronic medical records of The Ohio State College of Optometry may be done to identify possible subjects who then may be contacted by email or phone with information about the study. Word of mouth referrals by study team members to OSU employees and friends may occur. Emails to alumni of the OSU College of Optometry may be sent for local doctors to notify eligible potential subjects about the study.

Inclusion criteria:

- Subjects must be current Biofinity® spherical lens wearers.
- Subjects must have 20/25 or better distance visual acuity with current lenses.
- Good general health (defined by medication use that has not changed within the last month and the absence of medical conditions or treatments that are deemed confounding to the data as determined by the PI)
- Ability to give informed consent
- Willing to spend time for the study. Subjects will be required to attend three study visits and wear contact lenses on days between study visits.
- Either gender
- Any racial or ethnic origin
- 18 to 40 years of age.

Exclusion criteria:

- No current ocular inflammation or infection as assessed by the study investigator
- Pregnant or lactating females

Consent and Confidentiality

A team member trained in the consent process will provide the consent document for the potential subject to read and will review the procedures with reference to the consent form. The individual will be given provided time to read the consent form and offered the opportunity to ask questions. Participants will be explicitly told that they may stop participation at any time. All subjects will have the capacity to give informed consent. If there is any doubt as to the subject's ability to consent to the study, the subject will be excluded from the study. If the subject agrees to take part in the screening or measurement, he or she will sign and date the most recent IRB-stamped consent as will the team member. The subject will be provided with a copy of the consent form.

The investigator team is trained in privacy issues and will be reminded of the importance of patient privacy prior to study initiation. Potential study participants will contact us after seeing advertisements, emails or hearing about the study by word of mouth, giving them the choice of whether or not they wish to participate in a study for people with dry eyes. Privacy is protected by limiting information related to study recruitment only, and no other personal or medical information that should be private to the patients. The PHI needed is only for the purposes of this study. It is highly unlikely, indeed extremely remote that the dry eye symptoms or signs are related to private or personal information that should or would be preferred to be kept confidential to the patients. Risk factors for dry eye rarely relate to matters

or conditions that would be personal to the patient such as personal relationships, behaviors or diseases that one prefers to keep private and confidential.

Statistical Analysis and Power Calculation

This small sample size of 30 was chosen for convenience, as this study is not intending to prove superiority, but to study the acceptability of the study lens in previous successful Biofinity® wearers.

Data Management and Security

During the active stages of the study (recruitment to last measurement visit), all paperwork (consents, questionnaires and data forms) for each subject will reside in a subject folder for easy access throughout the study. The folders will reside in the limited-access research area, in a locked file drawer or cupboard. At the completion of the study or disenrollment of a subject the paperwork in the subject's folders will be reorganized into a regulatory binder (consents, W-9s) and a data binder (questionnaire and data forms) and will reside in an office in the limited-access research area. When the data analysis is completed and the study is considered complete, the binders will be stored in the secure Department or Office Clinical Research Area. Paperwork (questionnaire and data forms) for individuals who participate in the baseline visit but are not eligible to continue the study will be stored in the study regulatory binder in an office in the limited-access research area. An electronic file of potential subjects and a file of enrolled subjects with their contact information, as well as electronic files of collected data with the subject number, will reside on a limited-access shared drive with firewall and password protection and is restricted to individuals in the research team. Any electronic data files that contain PHI will be destroyed at the conclusion of the study.

Risks to Subjects and Mitigation

Although rare, a subject could experience eye pain, changes in vision, continued redness or irritation of the eye when inserting or learning to insert a contact lens. More likely transient blurring of vision (less than one minute) or mild, transient (less than a minute) stinging may occur.

Adverse Events

All adverse events will be documented and reported under the guidelines of The Ohio State University Event Reporting guidelines, with any serious, unanticipated and related events being reported to the IRB, by the PI, within 10 days. Adverse Events information will be summarized in the annual report to the IRB at the end of the study. Adverse events will be assessed and determined by [name].

Subject Dismissal

Subjects who, after study team member coaching, are not able to provide analyzable data may be dismissed from the study. Data may not be analyzable if patient isn't able to stand or move freely to utilize

the equipment, to name just two causes issues. These issues are usually revealed at the screening assessment visit. Subjects who cannot provide analyzable data will be dismissed for the study. Subjects who do not keep scheduled visits within the required time frame will be dismissed from the study. Study team members will make reasonable efforts to accommodate subjects' schedules.

Protocol Violations, Discontinuation

In the event that a member of the study team or a representative of sponsor becomes aware of a major protocol violation, the IRB shall be notified within 10 working days.

Timeline

IRB submission and approval → Recruitment and Data collection → Data processing and analysis → Final report
6-8 weeks Months 3-4 Month 5 Month 6

References

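### No CLDEQ-8 or VAS is specified on Biofinity, so change after the refit cannot be estimated and the Visit 3 scores have no stated reference for acceptability

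*Combined protocol and SAP*

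**What the plan says.** Under Key Endpoints, the CLDEQ-8 endpoint is "Subjective assessment of P1 with CLDEQ-8". The VAS endpoint names the symptoms but neither a lens nor a visit. The third endpoint is a questionnaire on quality of life, preference and lens modality.

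Under Study Time Points:

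- **Visit 1.** "Biofinity® lenses will be evaluated and optimized before dispensing a new pair of lenses for approximately 1 week of wear". Subjects also confirm that they are happy with their lenses.
- **Visit 2, before the refit.** "Patients will verify that they are still satisfied with their current Biofinity® contact lenses in order to proceed". Vision, fit and ocular health are checked.
- **Visit 2, after the PRECISION1 fit.** Subjects "will complete assessments of initial satisfaction, initial comfort, and initial vision using REDCap".
- **Visit 3, about 2 weeks later.** "Subjects will then complete surveys about their lens wear experience". The survey list comes directly after this. Its lead-in, "Surveys will be completed using REDCap and include", names no visit, and its last item is satisfaction with PRECISION1.

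The section Statistical Analysis and Power Calculation gives a convenience sample of 30 and says that "this study is not intending to prove superiority, but to study the acceptability of the study lens in previous successful Biofinity® wearers". It states no threshold, reference value or analysis of change.

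**The concern.** The aim is acceptability among people who were doing well in Biofinity. The protocol spends a visit and about a week of wear standardising that lens, yet takes no score on the scales of two of its three key endpoints at the end of that week. Suppose mean comfort at Visit 3 is 78 out of 100 (a hypothetical value). It could be better than, equal to or worse than what the same people would have reported for Biofinity, and the plan offers neither their own earlier score nor an outside benchmark to tell which.

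The satisfaction check on Biofinity does not fill the gap. No response format is given, and because it decides who proceeds, everyone who is refitted has passed it. Used as a pass/fail item, it does not vary among the subjects analysed. The Visit 2 REDCap ratings come after the new lens is fitted, so they are first impressions of PRECISION1 and not a baseline.

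**Working it through.** **Step 1: what is measured on which lens (Study Time Points).**

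| Time | Lens | Patient-reported wear experience | CLDEQ-8 or VAS specified |
|---|---|---|---|
| Visit 1 | Biofinity | Confirms being happy; no scale | No |
| Visit 2, before refit | Biofinity, about 1 week in a new pair | Confirms still satisfied; condition to proceed | No |
| Visit 2, after refit | PRECISION1 | Initial satisfaction, comfort, vision | Not named |
| Visit 3 | PRECISION1, about 2 weeks | Full survey list | Yes |

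The mean paired change is the PRECISION1 mean minus the Biofinity mean in the same subjects. The second term is not collected, so the change is not estimable at any sample size. The sample size of 30 rests on no formula, so there is no planned figure to reproduce.

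**Step 2: what the plan as written can estimate.**

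- *Visit 3 mean.* The 95% CI half-width is t(0.975, 29) × SD / √30 = 0.373 × SD. For an assumed VAS SD of 15 to 25 that is 5.6 to 9.3 points.
- *Share satisfied at Visit 3*, if the item is read as yes/no (an assumption, since no format is given). Exact 95% CIs for two hypothetical results: 24/30 gives 61.4% to 92.3%; 30/30 gives 88.4% to 100%.

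**Step 3: what a Biofinity score at Visit 2 would add.**

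Half-width = t(0.975, n−1) × SD × √(2(1−r)) / √n, where SD is the single-visit SD and r the correlation between visits. Both are assumed, as is n = 24. The last case allows for lost pairs, which the Subject Dismissal section makes possible: "Subjects who do not keep scheduled visits within the required time frame will be dismissed from the study".

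| Complete pairs | Multiplier of the SD of change | VAS, SD 15, r 0.7 | VAS, SD 25, r 0.3 |
|---|---|---|---|
| 30 | 0.3734 | 4.3 | 11.0 |
| 24 | 0.4223 | 4.9 | 12.5 |

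At SD 20 with 30 pairs, r of 0.3, 0.5 and 0.7 gives 8.84, 7.47 and 5.78 points. The protocol gives neither the scale range nor the SD of the CLDEQ-8, so for that instrument the result is in single-visit SD units: 0.44, 0.37 and 0.29 at the same three correlations.

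**Step 4: regression to the mean in that paired change.**

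Only subjects satisfied with Biofinity at Visit 2 go on, so their Biofinity scores would tend to be high on that day. If a proportion p passes and passing depends wholly on the score concerned, the expected shift against PRECISION1 is φ(z)/p × SD × (1−r), where z is the normal cut-off for p. With p = 0.8, φ(z)/p = 0.350, so at SD 20:

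- r = 0.3: 0.350 × 20 × 0.7 = 4.9 points
- r = 0.5: 0.350 × 20 × 0.5 = 3.5 points
- r = 0.7: 0.350 × 20 × 0.3 = 2.1 points

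For that p and SD these are upper bounds, because the satisfaction check will not depend on one score alone. They are not maxima over all inputs: SD 25 with r 0.3 gives 0.350 × 25 × 0.7 = 6.1, and a 70% pass rate with SD 20 and r 0.3 gives 7.0.

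**The case against.** The strongest reply is that the plan never claims the missing quantity. Its purpose is to explore experience after the refit, its CLDEQ-8 endpoint is worded for PRECISION1, and it disclaims superiority. A single-arm descriptive study is consistent with that. This stands as far as it goes: there is no contradiction in the plan, and it is not faulted for lacking a superiority test. But scores meant to show acceptability still need something to be read against.

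Second, the lead-in to the survey list names no visit and the VAS endpoint names no lens, so a Biofinity administration may have been intended. That is possible. Visit 3 only is the natural reading for the VAS, not an explicit statement. If more was intended, the protocol needs to say so.

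Third, acceptability is partly answered already: satisfaction with PRECISION1 among confirmed satisfied Biofinity wearers, preference and convenience, and clinical findings on both lenses. That also stands. It narrows the gap to the CLDEQ-8 and VAS but does not make those two scales interpretable.

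Fourth, the paired change would itself be imperfect. At SD 20 the regression bound is 36% of the CI half-width at r 0.7 (2.1/5.78) and 55% at r 0.3 (4.9/8.84), before open-label wear and fixed order are considered. A paired change also sets no rule for what is acceptable. These are good reasons to keep the comparison descriptive, but an imperfect reference is still more informative than none.

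**Conclusion.** The concern holds and should be fixed. No CLDEQ-8 or VAS measurement on Biofinity is specified, and no threshold or benchmark replaces it. The consequence is a limit on interpretation for two of three key endpoints; the study can still address its aim through the satisfaction, preference and clinical findings.

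The core conclusion rests on reading the schedule and needs no numerical assumption beyond taking the survey list as belonging to Visit 3. The figures for precision and regression to the mean show what the remedy would deliver. They rest on assumed SDs, correlations, pass rates and numbers of pairs; only the sample size of 30 comes from the protocol. Confidence is medium, because the survey schedule is not fully explicit.

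**What to change.** 1. State which survey is given, about which lens, at which visit.
2. At the start of Visit 2, before PRECISION1 is fitted, give the same REDCap CLDEQ-8, the six VAS items and a scored satisfaction item, all referring to the Biofinity run-in.
3. Report the paired change from Visit 2 to Visit 3 descriptively, with 95% CIs and the number of complete pairs, beside the absolute Visit 3 scores, the share satisfied and preference. Make no superiority claim.
4. State the limits: open label, single arm, fixed sequence, selection for satisfaction with regression to the mean, and about 1 week on Biofinity against about 2 weeks on PRECISION1.

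A justified acceptability threshold set in advance for the Visit 3 scores would be another way to supply a reference and could be added, but the protocol gives no basis for choosing one.

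The cost is a few minutes of existing forms at a visit that already takes place, plus a short protocol and IRB amendment. No visits, staff or subjects are added. The downsides are slight questionnaire burden and a possible effect of repeating the questionnaire. The timing matters: once a subject has been refitted, a Biofinity score can be obtained only by recall.

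### The key-endpoint surveys are scheduled only at Visit 3 with no exit survey or reason-for-stopping item, so a subject who withdraws early because of PRECISION1 leaves little evidence on acceptability

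*Combined protocol and SAP*

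**What the plan says.** The Statistical Analysis and Power Calculation section sets the aim as "to study the acceptability of the study lens in previous successful Biofinity® wearers" and gives N = 30 as a convenience figure ("This small sample size of 30 was chosen for convenience"). It names no analysis set, denominator or missing-data rule, and no threshold for acceptability.

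Key Endpoints lists three items: the CLDEQ-8 on PRECISION1, a VAS survey of comfort, dryness and vision, and a questionnaire on quality of life, preference and lens modality.

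Study Time Points places PRECISION1 ratings at two visits:

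- **Visit 2 (fitting):** subjects "will complete assessments of initial satisfaction, initial comfort, and initial vision using REDCap". No scale is stated, and this comes before the lenses are dispensed for home wear.
- **Visit 3 (about 2 weeks, ± 3 days, after fitting):** "Subjects will then complete surveys about their lens wear experience". The survey list follows directly: CLDEQ-8, six VAS items, quality of life/preference/modality, convenience and ease of use, and satisfaction with PRECISION1.

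Consent and Confidentiality states: "Participants will be explicitly told that they may stop participation at any time". Subject Dismissal removes those who do not attend within the visit time frame. The section headed Protocol Violations, Discontinuation contains only a rule for notifying the IRB of major violations. The Adverse Events section requires every adverse event to be documented.

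**The concern.** In a single-arm study of acceptability, giving up the lens is among the most direct evidence available. Every subject has confirmed satisfaction with Biofinity twice, at Visits 1 and 2, and so has a satisfactory lens to go back to. Withdrawing after a poor experience is a plausible response, and it depends on the very outcome being measured.

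Take a subject who is fitted at Visit 2, dislikes the lens after a few days and withdraws. The schedule yields ratings made in the office before any day of wear. It yields no CLDEQ-8, no dryness or end-of-day score and no preference. Unless the problem is recorded as an adverse event, the text also gives no route by which the reason reaches the record, so a lens-related exit looks the same as one for scheduling. There is no second arm whose dropout could reveal or offset the selection. Scores and reasons that are not collected at the time cannot be recovered later.

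**Working it through.** **Step 1. What the schedule yields for each type of subject**

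| Subject | Visit 2 initial ratings | Visit 3 surveys | Reason for stopping |
|---|---|---|---|
| Wears PRECISION1 to Visit 3 | yes | yes | not applicable |
| Stops the lens, still attends Visit 3 | yes | possible; not excluded, not provided for | not specified |
| Withdraws from the study before Visit 3 | yes | no | only if recorded as an adverse event |

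The gap is the third row.

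**Step 2. Inputs**

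- N = 30, from the Statistical Analysis section. The plan gives no alpha, power, effect size, SD or dropout rate, so there is no calculation behind 30 to reproduce. I take 30 as the number fitted at Visit 2; this is an assumption.
- Assumed: x = 24 favourable at Visit 3.
- Assumed: k lens-related withdrawals before Visit 3, all unfavourable, with k from 0 to 5.

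**Step 3. Percentage favourable**

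Among those who stayed the rate is x/(N − k). Among all fitted it is x/N. The difference equals the completer rate times k/N.

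| k | Stayed to Visit 3 | All fitted | Difference |
|---|---|---|---|
| 0 | 24/30 = 80.0% | 24/30 = 80.0% | 0 |
| 1 | 24/29 = 82.8% | 24/30 = 80.0% | 2.8 points |
| 3 | 24/27 = 88.9% | 24/30 = 80.0% | 8.9 points |
| 5 | 24/25 = 96.0% | 24/30 = 80.0% | 16.0 points |

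At k = 0 the 24 favourable are out of 30 who all attend, so nothing is lost.

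**Step 4. A score endpoint**

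Assume a mean comfort VAS of 80 in 27 completers and 40 in three withdrawals. The all-fitted mean is (27 × 80 + 3 × 40)/30 = 2280/30 = 76, against a reported 80: a shift of 4 points.

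**Step 5. What a denominator rule can and cannot do without exit data**

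If three subjects withdraw and their views are unknown, the all-fitted percentage lies between 24/30 = 80% (none favourable) and 27/30 = 90% (all favourable). Using all fitted as the denominator fixes the lower bound. Only a recorded reason or an exit survey narrows the range, and no denominator rule supplies the missing CLDEQ-8 and VAS scores.

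**Step 6. More subjects would not help**

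Keeping 30 completers at 10% loss needs 30/0.9 = 33.3, so 34 enrolled. The difference in Step 3 depends on the proportion lost, k/N, so it stays.

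**The case against.** Several stronger readings are tempting, and the documents do not support them.

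- **That the plan adopts a completers-only analysis.** It does not say so. It states no analysis set at all; describing only those who stayed is the default that follows from the schedule.
- **That the reason for stopping is never recorded.** Adverse events must be documented, and the risk section names eye pain, changes in vision and continued redness or irritation. Some lens-related exits would be captured that way. What remains is dislike, mild discomfort or unsatisfactory vision not recorded as an adverse event. The study's data forms and consent form are also not before us, so the claim is limited to what the protocol text specifies.
- **That stopping the lens means leaving the study.** Dismissal is for missed visits or unanalyzable data. A subject who stops wearing PRECISION1 could still attend Visit 3, although nothing asks for it.
- **That nothing can be repaired at analysis.** Counting all fitted subjects in the denominator gives a conservative bound with no new data (Step 5). Only the scores and the split between lens-related and unrelated exits are beyond recovery.
- **That the results are biased.** They are only if lens-related withdrawals occur, and the wear period is short.

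It is also fair to say that the initial comfort and vision ratings overlap in topic with the VAS endpoint. They still precede any day of wear and contain no dryness, end-of-day, CLDEQ-8 or preference item.

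On size, the exact 95% interval for 24/30 is 61.4% to 92.3%, so the 83% and 89% cases lie inside it. With an assumed VAS SD of 20, the standard error at n = 30 is 20/√30 ≈ 3.7, close to the 4-point shift. This means that the distortion may be no larger than the sampling error. It does not make it harmless, because it runs in one direction. No formal decision depends on the result, which keeps this a modest point.

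**Conclusion.** The point holds in a limited form. As written, a subject who withdraws from the study because of PRECISION1 before Visit 3 contributes no post-wear key-endpoint data, and contributes a reason only through adverse-event documentation. If such withdrawals occur and the Visit 3 summaries are reported on those present, they will tend to favour PRECISION1.

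The size cannot be determined from the documents. It is zero with no lens-related withdrawals. In the illustration it is about 3, 9 and 16 percentage points for one, three and five such withdrawals among 30 fitted. Those figures assume 24 favourable subjects and that every withdrawal is both lens-related and unfavourable, which is the worst case for a given number of withdrawals. The point is worth acting on because the lost information bears on the stated aim and must be collected when the subject stops.

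**What to change.** **Data collection.** In Study Time Points and in Protocol Violations, Discontinuation, add that any subject fitted with PRECISION1 who stops the lens or withdraws before Visit 3 is asked to complete the same REDCap surveys remotely, referring to the days the lens was worn. Add one item on the main reason for stopping (comfort, dryness, vision, handling, ocular finding, unrelated) and the stop date. Completion is voluntary, and the consent form says so. Subjects who stop the lens but stay in the study are still invited to Visit 3.

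**Reporting.** Give preference and satisfaction with all subjects fitted at Visit 2 as the denominator, and show lens-related stops as a separate category. Keep the Visit 3 CLDEQ-8 and VAS summaries as the main result. Beside them, as a sensitivity analysis, show the results including early-exit scores, because those scores cover a shorter wear period.

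**Cost.** One REDCap trigger, a reason item, a date field, and a sentence each in the protocol and consent form. The surveys are already in REDCap, and consent is already planned by phone and REDCap, so no extra visit, staff or subjects are needed. The downsides are that some withdrawing subjects will decline and that the reported acceptability may be slightly less favourable.

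### Team members may refer friends and employees into an uncontrolled open-label study whose key endpoints are all self-reported, and no exclusion or record of recruitment source limits the possible favourable-response bias

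*Combined protocol and SAP*

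**What the plan says.** The Recruitment section lists several routes: posters, emails, advertisements, bus signs, a records search and emails to alumni. It adds one personal route: "Word of mouth referrals by study team members to OSU employees and friends may occur". No cap is placed on it, and nothing says that the route by which a subject arrived will be recorded.

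The Exclusion criteria have two entries, one for ocular inflammation or infection and one for pregnancy or lactation. Neither concerns study staff, their colleagues, family or friends.

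On design, the Study Overview says: "This open-label study is of current Biofinity® (Cooper Vision, San Ramon, CA, USA) contact lens wearers who are satisfied with their lenses". All of them are then refit into the study lens, and no concurrent control is described.

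The Key Endpoints are "Subjective assessment of P1 with CLDEQ-8", a visual analog survey of comfort, dryness and vision, and "Assessment via questionnaire about quality of life, preference, and lens modality experience". All three come from the subject.

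The Statistical Analysis and Power Calculation section gives a convenience sample of 30 and names acceptability of the study lens, not superiority, as the aim.

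**The concern.** When the endpoint is the subject's own rating and the subject knows which lens is under study, a tie to the team is a recognised reason for a kinder answer. A randomised control would share much of that kindness, so that a comparison could partly cancel it. This design has no such comparison. Any courtesy in the ratings goes straight into the estimate of acceptability, and a confidence interval would not reveal it, because the interval reflects sampling error only.

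The plan also leaves no means of looking for the effect afterwards. If recruitment source is not captured, no one can later show the results without the referred subjects. This is a stated permission that is cheap to narrow, in a study whose result consists of these answers.

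**Working it through.** No figure in the plan is in dispute. The sample size of 30 cannot be reproduced, since no alpha, power, effect size, standard deviation or margin is given. The check is therefore a reading of the text, followed by an illustration on assumed values.

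**Reading of the text**

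1. *Could a control arm absorb the bias?* No. Every subject receives the study lens.
2. *Could a paired baseline absorb it?* None is described. Under Study Time Points, subjects confirm at Visits 1 and 2 that they are satisfied with the habitual lens. The initial ratings at Visit 2 follow the fitting of the study lens. The CLDEQ-8 and VAS surveys are set out after Visit 3. A baseline would in any case help only in part, since preference and satisfaction with the study lens are direct verdicts on it.
3. *Are answers shielded from the team?* The plan says "Surveys will be completed using REDCap and include" a list of instruments. It does not say that answers are private from visit staff. The Data Management and Security section keeps questionnaires in a folder for each subject, together with the consent. It is unclear whether that covers the electronic survey answers.
4. *Could the effect be examined later?* Not as written, because recording of recruitment source is not mentioned.

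**Illustration (share, bias and SD are all assumptions)**

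Shift in the mean of one VAS item = share referred × bias per referred subject.

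- 10% referred (0.10 × 30 = 3 subjects), 10 points: 0.10 × 10 = 1.0 point
- 30% referred (0.30 × 30 = 9 subjects), 10 points: 0.30 × 10 = 3.0 points
- 50% referred (0.50 × 30 = 15 subjects), 10 points: 0.50 × 10 = 5.0 points
- 50% referred, 15 points: 0.50 × 15 = 7.5 points

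For comparison, the 95% half-width of a mean is t(0.975, 29) × SD / √30, with t = 2.045:

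- SD 15: 2.045 × 15 / √30 = 5.6 points
- SD 20: 2.045 × 20 / √30 = 7.5 points
- SD 25: 2.045 × 25 / √30 = 9.3 points

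The shift runs from well inside the sampling error to about its size. It gets there only under the larger assumptions, such as half the sample being referred.

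For a percentage result such as preference, one subject is 1/30 = 3.3 points, so three altered answers would move it by 3/30 = 10 points. The normal-approximation half-width, 1.96 × √(p(1−p)/30), is 17.9 points at p = 0.5 and 14.3 points at p = 0.8. The 3.3-point figure describes only how coarse a sample of 30 is. It is no evidence that any answer would change.

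**The case against.** The case against has real force.

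- **Who receives the answers.** A reader might infer that subjects give their ratings to someone they know. The documents do not say so. Surveys go into REDCap, and nothing says that the referring team member runs the visit or sees the answers as they are given. This stands: the risk is possible, not shown.
- **Who the friends are.** The sentence does not say whose friends are meant or how close they are, and employees of a large university need not know the team. Referral is optional and is one route among several. This stands, and it is why other employees and students should stay eligible.
- **Direction.** A reader might infer that the mean VAS would be inflated upward by a known amount. Two of the six VAS items concern dryness, the direction of scoring is not stated, and no mean across items is defined. Only a shift in the favourable direction, item by item, can be argued.
- **Ratings alone.** A reader might infer that nothing else is measured. At Visit 3, "Subjects will have visual acuity, an assessment of ocular health, and lens fit completed". These measures are not key endpoints, so the point about the key endpoints survives. CLDEQ-8 and the VAS are symptom ratings, subjective but more than mere opinion.
- **Retention and expectations.** That tied subjects are likelier to stay in the study, or to know what the team hopes for, is plausible but has no support in the documents.
- **The wider limitation.** Unmasked rating without a control affects all 30 subjects, however recruited. Removing friends leaves that in place. This also stands: the fix removes an avoidable addition to the problem, not the problem.
- **Consequence.** With no acceptability threshold in the plan, no conclusion can be shown to flip.

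The Consent and Confidentiality section says that people who hear by word of mouth contact the team themselves. That answers a worry about pressure to enrol, but not one about how they respond.

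**Conclusion.** The concern holds in a limited form. The plan expressly permits team members to refer friends and employees, excludes no one tied to the team, and rests its key endpoints on self-report in an uncontrolled open-label design with no described survey on the habitual lens. A favourable-response bias is therefore possible, and as written it could be neither separated from real acceptability nor examined afterwards.

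Its size cannot be determined from the documents and may be negligible. The illustrative range of 1.0 to 7.5 VAS points rests wholly on an assumed referred share of 10% to 50% and an assumed bias of 10 to 15 points per referred subject. Priority is low to moderate, given the exploratory aim.

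**What to change.** 1. In the Recruitment section, remove friends from the sentence on team-member referral.
2. Add one exclusion: study team members, staff and students of the research group running the study, and their family members and close personal friends, as declared by the subject at screening. Self-declaration makes an otherwise loose category workable. Leave other university employees and students eligible.
3. Record recruitment source for every subject on the enrolment form.
4. Report the key endpoints with and without any team-referred subjects. With so few subjects this comparison is descriptive, but it lets a reader see whether the result leans on them.

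The cost is one exclusion bullet, one data field and one extra descriptive table. The downside is the loss of a minor recruitment channel in a narrow population (satisfied spherical-lens wearers aged 18 to 40 with 20/25 acuity or better), with recruitment and data collection planned for Months 3 to 4. Posters, emails, advertisements, bus signs, the records search and alumni emails all remain.
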